We anticipate enrolling a total of 70 adult women scheduled to undergo a laparoscopic Hysterectomy. Power calculation was based on a previous study which assessed recovery time in total laparoscopic hysterectomy and supracervical laparoscopic hysterectomy²⁰. Using a study power of 90% and an alpha level of 0.05, we concluded that we would need 28 patients for each tissue extraction group (vaginal extraction and mini-laparotomy) in order to detect a mean difference of 5 days in return to daily activities, and an additional 14 patients to account for anticipated 25% loss to follow-up. This will be a multi-center trial with surgeons participating at Brigham and Women's Hospital, Faulkner Hospital and Massachusetts General Hospital. Our goal for enrollment is 70 subjects with the first 35 subjects included in a mid-point analysis.

Inclusion criteria include women 18 years of age or greater who are eligible to undergo laparoscopic Hysterectomy, as determined clinically by the operating surgeon. Other concomitant laparoscopic procedures will be

performed as indicated and at the discretion of the primary surgeon (e.g., lysis of adhesions or removal of an ovarian cyst).

In all cases, exclusion criteria will include suspected malignancy, medical illness precluding laparoscopy, inability to give informed consent, or allergy to indigo carmine or methylene blue dye.

Briefly describe study procedures. Include any local site restrictions, for example, "Subjects enrolled at Partners will not participate in the pharmacokinetic portion of the study." Describe study endpoints.

Subjects in this research study will undergo laparoscopic hysterectomy. Tissue extraction for hysterectomy patients will be performed via vaginal extraction with knife morcellation or mini-laparotomy incision with knife morcellation. All procedures will be performed within a containment system (bag). The choice of procedure will be determined clinically by the operating surgeon based on patient characteristics and patient preference.

Vaginal extraction with knife morcellation in bag

Vaginal extraction with knife morcellation will be done in the standard fashion with the specimen being placed in a containment bag with the addition of 5cc of either indigo carmine or methylene blue dye.

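### The 14 extra patients cover 20% loss to follow-up, not the stated 25%; at 25% loss, 70 enrolled leaves 52 or 53 evaluable patients, not the 56 required

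*Protocol*

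**What the plan says.** All the figures are in the sample-size paragraph of the protocol, under Research Design and Methods.

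- Design values: "Using a study power of 90% and an alpha level of 0.05".
- Number needed: "we would need 28 patients for each tissue extraction group (vaginal extraction and mini-laparotomy", a total of 56, "in order to detect a mean difference of 5 days in return to daily activities".
- Allowance for loss: "an additional 14 patients to account for anticipated 25% loss to follow-up".
- Enrolment, stated twice: "We anticipate enrolling a total of 70 adult women scheduled to undergo a laparoscopic Hysterectomy" and "Our goal for enrollment is 70 subjects with the first 35 subjects included in a mid-point analysis".

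No other section gives a different loss rate, a different target or another basis for the 14. The paragraph cites an earlier study of recovery time as its source, but states no standard deviation, test or sidedness.

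**The concern.** A loss rate is the share of enrolled patients who do not supply the outcome. Enrolment is therefore found by dividing the number needed by one minus that rate. The protocol appears to have multiplied the number needed by one plus the rate, which always gives too few.

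If so, the enrolment goal does not deliver the protocol's own 28 per group at the loss rate it expects, and the 90% power is overstated. The loss rate matters here because the primary outcome comes from a patient diary. Patients not fully recovered by the post-operative visit return it later in a pre-paid envelope, prompted by a telephone reminder. Patients whose diary never comes back may not be evaluable for the primary aim.

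**Working it through.** **Inputs, all from the sample-size paragraph:** 28 per group (56 in total), 14 extra patients, 25% anticipated loss, 70 enrolled, 5-day difference, 90% power, alpha 0.05.

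**1. Reproduce the protocol's figure.** Multiplying by one plus the loss rate gives 56 × 1.25 = 70, so the extra patients are 0.25 × 56 = 14. This matches the text exactly.

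**2. Loss that the 14 actually cover.** 14/70 = 20%. Check: 70 × 0.80 = 56.

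**3. Evaluable patients at the stated 25%.** 70 × 0.75 = 52.5, so 52 or 53 patients, or 26.25 per group if equal. That is 3 or 4 short of 56.

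**4. Enrolment that would hold 56 at 25% loss.** Required number / (1 − loss) = 56/0.75 = 74.7, rounded up to 75 (75 × 0.75 = 56.25). By group, 28/0.75 = 37.3, rounded up to 38, so 76 in total (76 × 0.75 = 57). That is 19 or 20 extra patients instead of 14.

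**5. Effect on power.** The protocol gives no standard deviation (SD), so I solved for the value that makes its sample size consistent with 90% power. I assumed a two-sample t test with equal groups, a difference of 5 days and noncentral-t power, where the noncentrality is 5 / (SD × √(2/n)) on 2n − 2 degrees of freedom, with n per group. Two cases bound the rounding of 28: it gives exactly 90%, or it was rounded up from just above 27.

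| Two-sided 0.05 | SD (days) | 28 per group | 26.25 per group | 26 per group |
|---|---|---|---|---|
| 28 gives exactly 90% | 5.67 | 90.0% | 88.0% | 87.7% |
| 28 rounded up from just above 27 | 5.56 | 91.0% | 89.1% | 88.8% |

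The drop is 2.0 to 2.3 points in the first case and 1.9 to 2.2 points in the second. In the first case the difference detectable with 90% power rises from 5.0 to about 5.2 days.

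**6. Sensitivity.** With a one-sided 0.05 test and the same method, the drop is 1.7 to 2.1 points across both cases. A normal approximation gives an implied SD of 5.77 days (two-sided) and 87.8% to 88.1% power with 26 to 26.25 per group, which is the same picture.

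Steps 1 to 4 do not depend on the SD, the test or the sidedness. Only steps 5 and 6 do.

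**The case against.** The best defence is that the text does not say what the 25% is a percentage of. Read as an add-on to the required number, 56 + 14 = 70 is consistent. This does not rescue the sentence: it describes an anticipated loss to follow-up, which ordinarily means the fraction of enrolled patients lost. Rounding cannot account for a gap of 5 patients either.

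Three other points have weight.

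- **The effect is small.** In the rounding case, power ends only about one point below the nominal 90%, and the 25% is itself only an expectation. This limits the finding to a minor one but does not remove it.
- **Equal groups are assumed, not secured.** The protocol states: "The choice of procedure will be determined clinically by the operating surgeon based on patient characteristics and patient preference". An uneven split could cost as much as the inflation error or more. As an illustration, 56 evaluable patients split 37 to 19 give 86.6% power at an SD of 5.67 days. Correcting the allowance, even by enrolling 75 or 76, would therefore not guarantee 28 in each group.
- **The tenths of a point are softer than they look.** They rest on a back-solved SD. About 2 points is what the material supports.

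**Conclusion.** The concern holds. By plain arithmetic on the protocol's own figures, the allowance covers 20% loss and not 25%. At 25% loss the expected number of evaluable patients is 52 or 53 against 56 required.

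The consequence is minor: a loss of about 2 points of power, assuming equal groups, a t test and an SD inferred from the protocol's own sample size. No endpoint or analysis is affected. What needs correcting is a sentence that claims protection against a loss rate the enrolment goal does not cover.

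**What to change.** Restate the sentence so that its figures agree, in one of two ways:

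1. State that 70 enrolled allows for 20% loss to follow-up. This is suitable only if the investigators consider 20% realistic, since they now expect 25%.
2. Keep 25%, state that about 52 evaluable patients are expected, and give the power recomputed from the SD taken from the cited study. It should come out slightly below 90%.

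Either way the cost is one sentence, with no change to conduct or enrolment. The price is a slightly less favourable loss allowance (option 1) or power (option 2). Raising the goal to 75, or 76 for equal groups, is an alternative if the investigators prefer to keep both the 25% and the 56. It means 5 or 6 more patients, and it still leaves the split between the groups to clinical choice.

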**PARTNERS HUMAN RESEARCH COMMITTEE
PROTOCOL SUMMARY**

Answer all questions accurately and completely in order to provide the PHRC with the relevant information to assess the risk-benefit ratio for the study. Do not leave sections blank.

PRINCIPAL/OVERALL INVESTIGATOR

[name], PhD, MPH

PROTOCOL TITLE

A Partners prospective study assessing the perioperative outcomes of common methods of minimally invasive contained tissue extraction

FUNDING

None

VERSION DATE

1/13/2016

SPECIFIC AIMS

Concisely state the objectives of the study and the hypothesis being tested.

The goal of this study is to compare common methods of tissue extraction at the time of minimally invasive surgery, including vaginal extraction and mini-laparotomy; both performed within a containment system. The primary aim is to assess return to normal daily activities after each of the surgical techniques. Return to daily activities will be recorded on a post-operative patient activity diary recording the following tasks: a) work (if applicable), b) domestic tasks, c) driving a vehicle (if applicable) and d) physical exercise (if applicable). Additional information regarding post-operative pain (measured on a Likert scale), potential complications of each technique, such as tearing of the bag or leakage, and peri- and post-operative outcomes will be collected.

BACKGROUND AND SIGNIFICANCE

Provide a brief paragraph summarizing prior experience important for understanding the proposed study and procedures.

Laparoscopic approaches to gynecologic surgery are generally accepted as enabling superior visualization of the abdomino-pelvic cavity, smaller incisions, reduced blood loss and decreased recovery time relative to surgeries performed via laparotomy^{1, 2, 3}. A common method of tissue extraction is laparoscopic power morcellation. Power morcellation systems have been

frequently employed in laparoscopic surgery, and effectively core the desired tissue into pieces that are small enough to be removed via the cannula in laparoscopic trocar ports.

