On 4/17/14 the FDA issued a statement discouraging the use of power morcellation. The FDA released further guidance on 11/24/14 that encourages alternatives to laparoscopic power morcellation for women with symptomatic uterine fibroids, such as vaginal or abdominal specimen removal and laparotomy using a smaller incision (mini-laparotomy). Given the recent limitations on use of power morcellation, manual morcellation via vagina or minilaparotomy with use of a knife blade are the only options which allow for large specimen removal at the time of minimally invasive surgery. This study will compare two methods of manual morcellation: vaginal extraction and mini-laparotomy incision. Although the techniques for vaginal or minilaparotomy morcellation have not typically involved use of a containment bag as standard of practice, we plan to perform all morcellation procedures within a containment bag system in an attempt to minimize any risks associated with tissue disruption or dissemination.

RESEARCH DESIGN AND METHODS

Briefly describe study design and anticipated enrollment, i.e., number of subjects to be enrolled by researchers study-wide and by Partners researchers. Provide a brief summary of the eligibility criteria (for example, age range, gender, medical condition). Include any local site restrictions, for example, "Enrollment at Partners will be limited to adults although the sponsor's protocol is open to both children and adults."

This study is designed as a prospective cohort study. The primary aim is to assess return to daily activities after the two methods of tissue extraction. Secondary aims include evaluating peri-operative outcomes and incidence of spillage of the morcellated tissue or fluids in the abdomen and pelvis.

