In all cases, following morcellation and removal of the bag, the abdomen and pelvis will be carefully examined for any signs of spillage of fluid, tissue or blue dye as well as the integrity of the containment system by the surgeon. After surgery the bag will be carefully examined for any tears or damage. The used bag will be emptied, washed, dried, and filled with blue dye-tinted fluid (indigo carmine or methylene blue). The bag will be filled to the level where it was inside the patient during morcellation, as noted by marking pen during morcellation process (ie: any portion of bag exterior to patient during morcellation process will not be assessed).

If there is leakage noted prior to morcellation, the specimen will be removed and a new containment system will be replaced. If there is trauma to surrounding structures (bladder, bowel, blood vessels) during morcellation, the procedure will be discontinued. Conversion to laparotomy may be performed to repair these structures.

After Surgery

After surgery, patients will complete a report of their recovery symptoms in a diary including a report of pain, medication use and activities. They will fill out this diary daily until their post-operative visit or the day they return to perform their activities (work, household chores, driving and exercise) without limitations (exactly the same way they used to do before surgery, as determined by a pre-operative baseline diary), an estimated 2-4 week time frame.

Post-operative Visit

As per routine post-operative care, the patients will return for a post-operative office visit between 2 and 6 weeks after surgery. This will include a

discussion of recovery and exam as appropriate. Patients will return their diary at this time if they have returned to normal activities.

Follow-up

Patients who had not yet returned to all of their activities by the post-operative visit will receive a package either in person or in the mail including a pre-paid envelope for them to return when they have resumed all activities. A phone call reminder will be made 2 weeks after sending the package.

All data will be analyzed using SPSS. A member of the team (such as a research assistant who has been trained in HIPPA procedures) will be in charge of abstracting data from the medical records and entering this information into a study database.

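### Pain and medication recording stops when a woman resumes her activities, so route comparisons of these items from about week 2, or over the whole diary, are open to informative truncation

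*Protocol*

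**What the plan says.** Under Research Design and Methods, After Surgery, the protocol states that "patients will complete a report of their recovery symptoms in a diary including a report of pain, medication use and activities". The stop rule follows at once and covers the whole diary: "They will fill out this diary daily until their post-operative visit or the day they return to perform their activities". The return in question is to work, household chores, driving and exercise at the pre-operative level. Expected duration is "an estimated 2-4 week time frame".

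Under Post-operative Visit, "the patients will return for a post-operative office visit between 2 and 6 weeks after surgery". Diaries are handed in then if normal activities have been resumed. Under Follow-up, women who have not resumed everything receive a package "including a pre-paid envelope for them to return when they have resumed all activities".

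On the status of the outcomes, Specific Aims says "The primary aim is to assess return to normal daily activities after each of the surgical techniques". Pain appears in the same section as a supporting item: "Additional information regarding post-operative pain (measured on a Likert scale". Research Design and Methods does not name pain among the secondary aims: "Secondary aims include evaluating peri-operative outcomes and incidence of spillage of the morcellated tissue or fluids in the abdomen and pelvis". No pain day or pain summary is fixed. The lists of intraoperative and medical-record data contain no pain score or post-operative medication item, so the diary is the only described source. Expected Benefits hypothesises earlier return after vaginal extraction.

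**The concern.** The stop rule suits the activity items, because once a woman has resumed everything there is nothing left to record. It does not suit pain and medication use, which can continue after that day. On any later day, the women still scoring pain are those who have not yet recovered. If vaginal extraction brings earlier return, that remaining group is smaller and more selected on the vaginal side.

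Two kinds of comparison are exposed. The first is a same-day comparison late in follow-up: if slower recoverers also have more pain, the remaining vaginal scores are pushed up more, and a real pain advantage shrinks. The second is an average or total over each woman's own diary, because the periods being averaged or totalled differ by route.

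This is a data-collection rule, not an analysis detail. An analysis plan can choose which days to compare, but it cannot restore days that were never recorded, even if every diary is returned.

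**Working it through.** **Inputs from the protocol** (Research Design and Methods): 28 women per group, 90% power, alpha 0.05, mean difference 5 days. No SD is given, so the 28 cannot be reproduced independently; it can only be solved backwards for the SD.

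**Implied SD.** Taking alpha as two-sided (the protocol does not say), the two-sample t-test with 28 per group and 90% power needs a standardised difference of 0.882. SD = 5 / 0.882 = 5.67 days. The normal approximation gives 5.77.

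**Assumptions not in the protocol.** Return day is normal with SD 5.67. Mean return (vaginal v mini-laparotomy) is either 16 v 21 or 18.5 v 23.5; the second pair is centred on day 21, the middle of the 2-4 week estimate. The true pain difference is 1.0 point on every day, the pain SD is 2, and the correlation between pain and return day is ρ.

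**Formulas.** With a = (t − mean)/SD, the share still recording on day t is 1 − Φ(a). Among those women, mean pain is raised by ρ × 2 × λ(a), where λ(a) = φ(a)/(1 − Φ(a)). The observed difference (mini-laparotomy minus vaginal) is therefore 1.0 − 2ρ[λ(a_V) − λ(a_M)].

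**Day 14, means 16 v 21.** a = −0.353 and −1.235; shares 64% v 89%; λ = 0.588 and 0.209, gap 0.379. For ρ = 0.3: 1 − 0.6 × 0.379 = 0.77. For ρ = 0.5: 0.62. For ρ = 0.7: 0.47.

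**Day 14, means 18.5 v 23.5.** a = −0.794 and −1.676; shares 79% v 95%; λ = 0.370 and 0.103, gap 0.267. The difference reads 0.84, 0.73 and 0.63.

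**Other days, means 16 v 21, same formula:**

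| Day | Still recording, vaginal v mini-laparotomy | λ gap | Observed difference at ρ = 0.3 / 0.5 / 0.7 |
|---|---|---|---|
| 3 | 98.9% v 99.9% | 0.026 | 0.98 / 0.97 / 0.96 |
| 7 | 94% v 99% | 0.101 | 0.94 / 0.90 / 0.86 |
| 14 | 64% v 89% | 0.379 | 0.77 / 0.62 / 0.47 |
| 18 | 36% v 70% | 0.541 | 0.68 / 0.46 / 0.24 |

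At ρ = 0 the observed difference is 1.0 on every day. If mean return is the same in both groups, the λ gap is zero and so is the bias.

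**Average over each woman's own diary.** This was simulated with 400,000 women per group: means 18.5 v 23.5, SD 5.77, visit uniform over days 14-42, diary closing at the earlier of visit and return, mean pain 6·exp(−t/10) + 0.5, between-woman SD 1.5. With no true pain difference, the own-diary averages differ by −0.35 points (mini-laparotomy minus vaginal), and a true 1.00 reads as 0.65. This holds even at ρ = 0, because longer diaries add low-pain late days. Over a fixed 28 days common to both groups the bias is 0.00.

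**The visit.** Read alone, the stop rule lets the visit close the diary. The Post-operative Visit and Follow-up text has unrecovered women keep material to send back once they resume, which suggests recording may go on. In the simulation this changes how many late scores exist (day 21: 25% v 50% recording if the visit stops the diary, 33% v 67% if it does not). It hardly changes the same-day bias: at ρ = 0.6 with no true difference, −0.49 against −0.50 on day 21.

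**The case against.** A reader might infer that the pain comparison as a whole is distorted. The documents do not support that. Under the less favourable pair of means above, day 3 keeps 0.96 to 0.98 of a true 1.0 and day 7 keeps 0.86 to 0.94. The protocol commits to no late-day mean, whole-diary average or medication total, and a later plan could choose an early fixed day and largely avoid the problem. That limits the point to late and whole-diary comparisons. It does not remove it, since nothing in the protocol confines the comparison to the early days.

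A reader might also infer that a slow recoverer records until her visit, as late as day 42, and then stops. The text does not settle this: the *or* in the stop rule does not say which event governs, and the pre-paid envelope points the other way.

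Three further objections stand. The pain SD, the correlations and the constant 1.0-point difference are all assumed, and the protocol does not give the range of its Likert scale. Means of 16 v 21 have 36% of vaginal women finished before day 14, which sits awkwardly with a 2-4 week estimate; the later pair gives less bias. And a diary that closes on full resumption of activities probably loses days of low pain and little medication, so the loss in medication totals may be small; it has not been estimated. Finally, pain is supporting information and not a named secondary aim.

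**Conclusion.** The point holds in limited form. The primary outcome sets how long pain and medication use are recorded. If return time differs by route, comparisons of these items from about week 2, or over each woman's own diary, are open to informative truncation. On day 14, under the stated assumptions, a true 1.0-point difference would read between about 0.5 and 0.8 for correlations of 0.7 down to 0.3, and 1.0 with no correlation. The own-diary average needs no such correlation to be biased; unequal return times are enough. Pain on a fixed day in about the first week is largely sound. The primary comparison is not affected. Whether the visit ends recording is an ambiguity to reconcile, not an established fault. This is a cheap improvement to a supporting outcome and not a threat to the study's main result.

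**What to change.** In After Surgery, and in the diary instructions, give the items separate stop rules. Leave the activity items as they are. Have every woman record pain and medication use daily through the same fixed post-operative day, whether or not she has resumed her activities. Day 14, the earliest visit date, fits the existing schedule. State that routes are compared on these two items only over that common period.

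Reconcile the stop rule with the Post-operative Visit and Follow-up text, so that it is clear whether a woman who has not resumed everything by her visit goes on recording, and which items.

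The cost is a short wording change and, for women who recover before the fixed day, two diary items for a few more days. Pain after the common day would not be compared between routes; a later day would cover more of recovery at the price of more diary burden.

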The following data points will be collected via the intraoperative data collection sheet: surgeon, patient MRN, date of surgery, hospital (BWH, FH, MGH), procedure (total hysterectomy, supracervical hysterectomy), approach (laparoscopic, robotic), method of tissue extraction (vaginal, mini-laparotomy), size and location of mini-laparotomy if applicable, indication (pain/endometriosis, abdominal bleeding, fibroids, prolapse, other), length of procedure (incision to close), time for morcellation (insertion of bag to removal of bag), type of bag (EcoSac, LapSac, Lahey Bag, EndoCatch, Anchor tissue retrieval, Alexis Contained Extraction System), use of bag protector, use of indigo carmine or methylene blue, bag breaking/tearing/leaking and spillage of dye or tissue fragments.

The following data points will be extracted from the medical record: race, age, gravidity, parity, BMI, prior abdominal surgery (LSC, Laparotomy, None), pathology, weight of specimen, chromopertubation, intraoperative complications and estimated blood loss, concomitant procedures, hand-assisted, cystoscopy (for hysterectomy), and adnexal surgery (for hysterectomy). Post-operative complications will be assessed 8 weeks after surgery and rated using the Clavien-Dindo scale. Outcome information including EBL >1000ml, bowel injury, bladder/ureter injury, transfusion, conversion to open, reoperation, readmission and length of stay will also be collected.

For studies involving treatment or diagnosis, provide information about standard of care at Partners (e.g., BWH, MGH) and indicate how the study procedures differ from standard care. Provide information on available alternative treatments, procedures, or methods of diagnosis.
--

On 4/17/14 the FDA issued a statement discouraging the use of power morcellation. The FDA document includes language that acknowledges the fact that surgeons have offered morcellation in closed systems (i.e. a bag) and it does not recommend against this technique. The most recent FDA

guidance released on 11/24/14 allows for uncontained power morcellation in women who are not peri- or post-menopausal.

Our study protocol is more conservative than the current FDA recommendations with the addition of a containment bag to minimize spread of tissue when performing manual morcellation with a knife blade.

Women who choose not to participate in this study will receive traditional care as determined appropriate by patient and physician discussion.

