Patients enrolled that undergo laparoscopic morcellation in a containment system (bag) may experience traditional benefits of minimally invasive surgery. These include, but are not limited to, lower incidence of complications, such as infection, hemorrhage, deep venous thrombosis and pulmonary embolism, incisional hernias, postoperative adhesions. We hypothesize that patients who have vaginal morcellation will experience earlier return to normal activities compared to mini-laparotomy. The effect on operating room times is unknown. Moreover, the results of our study may provide the investigators with valuable information to facilitate the creation of an ideal morcellation containment system to be used in future gynecologic laparoscopies. A greater understanding of alternatives to laparoscopic power

morcellation (vaginal extraction and mini-laparotomy incision) will be gained and may benefit future patients.

EQUITABLE SELECTION OF SUBJECTS

The risks and benefits of the research must be fairly distributed among the populations that stand to benefit from it. No group of persons, for example, men, women, pregnant women, children, and minorities, should be categorically excluded from the research without a good scientific or ethical reason to do so. Please provide the basis for concluding that the study population is representative of the population that stands to potentially benefit from this research.

The study population of women will be derived from the population that is seeking laparoscopic Hysterectomy at Brigham and Women's Hospital, Faulkner Hospital, and Massachusetts General Hospital. All cases of laparoscopic hysterectomies and myomectomies will be eligible. The first 35 eligible cases will comprise the subset for mid-point analysis. Patients with a known allergy to indigo carmine or methylene blue will be excluded from the recruitment.

This is the same population that stands to potentially benefit from this research.

When people who do not speak English are excluded from participation in the research, provide the scientific rationale for doing so. Individuals who do not speak English should not be denied participation in research simply because it is inconvenient to translate the consent form in different languages and to have an interpreter present.

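### The diary is handed in only after recovery and no final collection date is set, so slow recoverers are more likely to be missing from the primary outcome

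*Protocol*

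**What the plan says.** Protocol, Specific Aims: "The primary aim is to assess return to normal daily activities after each of the surgical techniques". The outcome is to be recorded in a patient diary, and no other source is named.

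Protocol, Research Design and Methods, sets out collection under three subheadings:

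- **After Surgery.** The diary is kept daily until the post-operative visit or the day of full return to activities, which is expected within 2-4 weeks. The wording lets a woman who has not recovered stop her entries at the visit.
- **Post-operative Visit.** The visit is loosely timed: "the patients will return for a post-operative office visit between 2 and 6 weeks after surgery". Handing in the diary depends on recovery: "Patients will return their diary at this time if they have returned to normal activities".
- **Follow-up.** A woman not yet back to all activities gets a package "including a pre-paid envelope for them to return when they have resumed all activities". The only chase is this: "A phone call reminder will be made 2 weeks after sending the package".

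No last collection date is given, and no incomplete diary or recovery status is requested from a woman who remains limited. The lists of data items in the same section do not include recovery status. The one fixed later time point serves another purpose: "Post-operative complications will be assessed 8 weeks after surgery".

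The sample size paragraph allows for "an additional 14 patients to account for anticipated 25% loss to follow-up" and does not relate that loss to recovery time. Expected Benefits gives the direction: "We hypothesize that patients who have vaginal morcellation will experience earlier return to normal activities compared to mini-laparotomy".

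**The concern.** Return of the diary is conditional on the event being measured, first at the visit and again by post. A woman who recovers before her visit hands the diary over in person. A woman who recovers later must remember to post it, possibly weeks afterwards, and one who never fully recovers is never asked for it. Unless postal return is as complete as return in person, the longest recovery times are the ones most likely to be missing.

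If mini-laparotomy is slower, as hypothesised, and the two SDs are similar, more of its diaries would be lost and its mean would be pulled down further. The observed difference would then probably shrink. Enrolling 14 more women restores the count but not the women who are selectively absent.

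This is a collection rule, so it cannot be left to the analysis plan. An analysis plan can choose a missing-data method, but it cannot recover diaries or later recovery status that were never requested.

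**Working it through.** **Inputs from the Protocol.** Difference 5 days; 28 per group; power 90%; alpha 0.05 (taken as two-sided); 25% loss; visit at 2-6 weeks. Total: 2 × 28 = 56, plus 56 × 0.25 = 14, gives 70, or 35 per group if the groups are equal.

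**Implied SD.** The Protocol gives none. From n = 2(z₀.₉₇₅ + z₀.₉₀)²σ²/δ², σ = 5 × √(28/2) / (1.960 + 1.282) = 5.77 days. Solving with the t-test gives about 5.67. I use 5.7.

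**Assumptions not in the Protocol.** Normal recovery times with means 21 (vaginal) and 26 days (mini-laparotomy). Every diary is returned if recovery precedes the visit; a fraction r is returned otherwise. Women without a diary are left out and the rest are compared by a pooled t-test.

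**One case by hand: all visits on day 28.**
- Share still unrecovered: vaginal, z = (28 − 21)/5.7 = 1.23, so 11.0%; mini-laparotomy, z = (28 − 26)/5.7 = 0.35, so 36.3%.
- Mean among those recovered by day 28, μ − σφ(z)/Φ(z): 19.80 and 22.64 days. With r = 0 the observed difference is 22.64 − 19.80 = 2.84, or 2.86 by simulation.
- Mean among the late recoverers, μ + σφ(z)/(1 − Φ(z)): 30.75 and 31.89 days. With r = 0.5:
  - vaginal: (0.890 × 19.80 + 0.055 × 30.75)/0.945 = 20.4
  - mini-laparotomy: (0.637 × 22.64 + 0.181 × 31.89)/0.819 = 24.7
  - difference: about 4.3 days

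**Simulation, equal SDs (20,000 trials per case).** With full return the difference is 5.0 days and power 95%.

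| Visit day | Late diaries returned | Observed difference (days) | Power | Power, random loss of the same size |
|---|---|---|---|---|
| 28 | 0% | 2.86 | 64% | 88% |
| 28 | 25% | 3.66 | 78% | about 90%* |
| 28 | 50% | 4.26 | 88% | 92% |
| 28 | 75% | 4.68 | 92% | – |
| Uniform 14-42 | 0% | 4.44 | 77% | 83% |
| Uniform 14-42 | 25% | 4.70 | 85% | 87% |
| Uniform 14-42 | 50% | 4.86 | 90% | 91% |
| 42 | 0% | 4.97 | 95% | – |

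*Overall loss is 0.75 × (11.0% + 36.3%)/2 = 17.7%, leaving 35 × 0.823 = 28.8 per group, close to the 28 that the Protocol sizes for 90%.

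The case nearest the Protocol's 25% loss is visits spread over 2-6 weeks with a quarter returned: loss is 20% against 32%, or (20 + 32)/2 = 26% overall.

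**Unequal SDs, a quarter to half returned, visits on day 28 or spread.** Vaginal 8, mini-laparotomy 4: the difference rises to 5.4-6.1 days. Vaginal 4, mini-laparotomy 8: it falls to 2.0-4.0 days.

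**Keeping every woman in the analysis.** A log-rank test on all 70 women (4,000 trials) has about 90% power when those unrecovered on day 28 are censored there, against 64% when they are left out of the t-test. It is also about 90% when everyone is followed to day 56.

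**The case against.** The strongest reply has four parts.

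1. *Status at the visit is already known.* The visit includes a discussion of recovery, and the site must know who has not recovered in order to send the package. A woman who attends and never posts her diary could be censored at her visit. This is partly right, and the log-rank result shows how much it would help. But status is not among the listed data items, and the visit says nothing about recovery afterwards.
2. *The larger losses come from leaving women out, which the Protocol does not prescribe.* True: it names only the software, and the choice of analysis may sit in an analysis plan. That limits the power figures. It does not supply data never collected.
3. *The effect is small in the likeliest setting.* With visits spread over 2-6 weeks and about 26% loss, the cost is 0.3 days and 2 points of power beyond random loss. With half returned it is about 0.1 days and 1 point, and with visits at day 42 almost nothing. The worst case needs every visit on day 28 and no diary posted despite envelope and call. SDs of 8 and 4 have no basis in the Protocol. All of this stands.
4. *The reminder is well placed.* If the package goes out at the visit, the call comes at about 4-8 weeks, when most women should have recovered. It will reduce the loss, but it is a single call, may still precede recovery, and records no status.

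That late recoverers will be missing more often is also an inference: it requires postal return to be lower than return in person.

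**Conclusion.** The concern holds, as a design weakness that should be corrected, with medium confidence about its size. The Protocol makes return of its only primary-outcome source depend on recovery and sets no end date.

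Under equal SDs and partial return, the three moderate cases (day-28 visits with half returned; spread visits with a quarter or half returned) give 4.3 to 4.9 days instead of 5.0. Their extra cost over random loss is 92 − 88 = 4, 87 − 85 = 2 and 91 − 90 = 1 points; repeat runs put the largest nearer 5. With day-28 visits it grows to about 12 points if a quarter are returned and to 88 − 64 = 24 points if none are.

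The direction is probably toward no difference if mini-laparotomy is slower and the SDs are similar. It is not assured: a more variable vaginal arm would exaggerate the difference. Return rates, visit days and SDs decide which case applies, and the Protocol fixes none of them. Without recovery status on women who return nothing, the investigators could not tell afterwards.

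**What to change.** - Collect the diary and a recorded recovery status from every woman at the visit, recovered or not.
- Collect both again at one fixed final date from every woman not recovered at the visit. Eight weeks is convenient, since complications are already assessed then. Use the existing pre-paid envelope and call, and word the instruction so that an incomplete diary is also returned.
- State that a woman who has not recovered at the visit continues her diary until she recovers or the final date arrives.
- Analyse time to return to activities as a time-to-event outcome, censoring women not recovered at their last known status instead of leaving them out.

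The cost is revised diary, envelope and reminder instructions and one added data item. The envelope and call stay the same, and neither the surgery nor the sample size changes. The small downside is that some women keep the diary longer.
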